### III. SUBJECT SELECTION

**Subjects:** All patients over the age of 18 who have a visit with a PCP at one of the intervention practices during the 2 years preceding the study period will be eligible. We are able to utilize data from the past 2 years stored in the EHR to identify CKD patients with uncontrolled HTN. The first inclusion criteria will be CKD, defined as two prior eGFR  $16-59$  mL/min/1.73m $^2$  separated by 90 days, as calculated by CKD-EPI, or two prior UACR  $>30$ mg/g. The second inclusion criteria will be uncontrolled hypertension, defined as at least one SBP  $>140$  mmHg within the 2 years preceding the enrollment visit, as well as SBP  $>140$  mmHg at the enrollment visit. Our objective was to include PCPs who have a consistent panel of primary care patients. We obtained a list of currently employed physicians, physicians assistants and nurse practitioners in our primary care network of 15 practices. We excluded residents in training, as well as physicians who were only seeing urgent care and walk-in patients.

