#### **Inclusion of Women and Minorities**

Women will be represented in this study, reflecting the patient population of the BWH primary care practices and the physician population of BWH; women comprise over 50% of patients in these practices. Minorities also are fully represented in this study in proportion to their presence in these primary care practices and in proportion to their presence in the BWH physician and specialist community. The practices serve an ethnically and socioeconomically diverse patient population. Approximately 16% percent of BWH patients are Latino and 29% are Black. About 1.5% of BWH patients are Asian. Definitions of patients' race and ethnicity will be based on self-report at the time of hospital registration. By promoting uniformly high standards of patient care, our interventions may lessen disparities in care.

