**Specific Aim 2 & 2a Procedures:**

**Setting:** The Brigham and Women's Primary Care Practice-Based Research Network (BWPC PBRN) is one of 155 PBRNs nationally certified by the Agency for Healthcare Research and Quality (AHRQ). The BWPC PBRN is a network of 15 practices which includes hospital-based practices, community-based practices, and community health centers affiliated with Brigham and Women's Hospital. The network includes 185 primary care physicians that care for approximately 150,000 patients.

**Subjects:** All patients over the age of 18 who have a visit with a PCP at one of the intervention practices during the 2 years preceding the study period will be eligible. We are able to utilize data from the past five years stored in the EHR to identify CKD patients with uncontrolled HTN. The first inclusion criteria will be CKD, defined as two prior eGFR 16-59 mL/min/1.73m^2 separated by 90 days, as calculated by CKD-EPI, or two prior UACR >30mg/g. The second inclusion criteria will be uncontrolled hypertension, defined as at least two SBP >140 mmHg within the 2 years preceding the study period. We will exclude all patients who are currently pregnant. The CDS will review lab data starting five years before the visit to determine whether the patient has CKD using the logic described above. If the patient has CKD, the CDS will search BP data starting one year before the visit to determine whether the patient has had at least two SBP > 140 mmHg.

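### The Aim 2a entry rule counts raised SBP readings rather than separate outpatient occasions, so one visit or one hospital stay can meet it; the CKD rule has narrower gaps of the same kind

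*Combined protocol and SAP*

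**What the plan says.** Eligibility is described in two places.

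**Section III, Subject Selection.** Records are searched over two years: "We are able to utilize data from the past 2 years stored in the EHR to identify CKD patients with uncontrolled HTN". CKD requires two eGFR values of 16-59, "separated by 90 days, as calculated by CKD-EPI, or two prior UACR" values above 30 mg/g. Uncontrolled hypertension requires at least one SBP above 140 "mmHg within the 2 years preceding the enrollment visit, as well as SBP" above 140 at the enrollment visit itself.

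**Section V, Specific Aim 2 & 2a Procedures, Subjects.** The record window becomes five years: "We are able to utilize data from the past five years stored in the EHR to identify CKD patients with uncontrolled HTN". The CKD definition is unchanged. Uncontrolled hypertension is now "defined as at least two SBP >140 mmHg within the 2 years preceding the study period". The operating logic follows. For kidney function, "The CDS will review lab data starting five years before the visit to determine whether the patient has CKD". For blood pressure, "the CDS will search BP data starting one year before the visit to determine whether the patient has had at least two SBP" above 140 mmHg.

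Neither place names a type of encounter for any qualifying value, and neither Aim 2a version of the SBP rule requires different days.

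Three other statements bear on the point. The Aim 1a procedures give the alert a field for a repeat BP, which is stored in the vital signs flowsheet. They also say that control patients are identified in silent mode by the same inclusion criteria as intervention patients. The section on implementation in Epic plans a review of 150 charts, 10 per clinic, to check that the rules pick the right patients.

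**The concern.** A requirement for two raised readings is meant to show that the elevation persists. It does so only if the readings come from separate occasions. Two values minutes apart share the same circumstances, and a hospital stay can produce many values within days, often under acute stress. A count of readings then stops measuring persistence.

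Aim 2a is meant to test the intervention in CKD patients with uncontrolled blood pressure. Patients whose usual clinic SBP is controlled have little SBP to lose, so enrolling them pulls the between-arm difference towards zero. The background section cites an average effect of just 1 mmHg for decision support in a non-CKD population, so there is little room for dilution. In the intervention arm, adding CKD to the problem list is a pre-checked default (Aim 1c), and Section VII acknowledges risks from CKD labelling and from overtreatment. A wrongly qualified patient is exposed to both.

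**Working it through.** **Step 1: test each rule against the scenarios.** The plan gives no figure to reproduce here, so the check is one of logic.

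| Rule | One visit, first and repeat reading | One hospital stay | What can still go wrong |
|---|---|---|---|
| SBP, Section III | Does not qualify: the other reading must precede the enrollment visit | Does not qualify alone: SBP must also exceed 140 at enrollment | An acute-care value can be the one prior reading |
| SBP, Aim 2a (both versions) | Qualifies | Qualifies, if acute values are searched | No raised enrollment-visit reading is required |
| eGFR, both sections | Does not qualify | A stay shorter than 90 days cannot qualify | Low values from two acute episodes at least 90 days apart |
| UACR, both sections | Depends on spacing | Qualifies if the 90 days applies only to eGFR | Spacing is not clearly attached |

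The Aim 2a SBP rule is therefore the main gap. The Section III rule and the eGFR rule are only partly open.

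**Step 2: is there a filter elsewhere?** None is stated. The chart review could reveal misfires, but the plan gives no setting or date standard to judge a chart against.

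**Step 3: illustration of direction (all inputs assumed).** The documents give no within-patient SD, number of readings or share of patients with acute stays. Let a patient with usual SBP m have k independent readings with standard deviation s. Then p = P(N(m, s) > 140), and P(at least two of k) = 1 − (1−p)^k − k·p·(1−p)^(k−1).

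| Usual SBP | p, s = 15 | 4 acute readings | 12 acute readings | p, s = 10 | 2 to 4 clinic readings |
|---|---|---|---|---|---|
| 120 | 0.091 | 4% | 30% | 0.023 | at most 0.3% |
| 125 | 0.159 | 12% | 59% | 0.067 | 0.4 to 2.4% |
| 130 | 0.252 | 27% | 85% | 0.159 | 2.5 to 12% |

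For example, at 125 with k = 12 and p = 0.159: 1 − 0.841^12 − 12 × 0.159 × 0.841^11 = 0.59.

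Under Section III with the same inputs, at least one of 12 acute readings exceeds 140 with probability 0.87 (usual SBP 125) or 0.97 (130). The enrollment reading must also exceed 140, with p = 0.067 or 0.159. The products are 0.87 × 0.067 = 0.06 and 0.97 × 0.159 = 0.15 per visit.

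**Step 4: dilution (illustrative only).** If a share f of enrollees cannot respond, the mean effect is multiplied by (1−f), and the sample needed for equal power by 1/(1−f)². For f = 5%, 10% and 20% this is 1.11, 1.23 and 1.56. If the filter removes these patients without replacement, the effect is restored but the sample falls to (1−f) of its size. The net gain in information is then 1/(1−f) = 1.05, 1.11 and 1.25. Both lines take the extreme case of no response at all and ignore clustering by clinician. No value of f comes from the documents.

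**The case against.** **Same-visit repeats.** The only repeat-reading route described is a field inside the alert. It is used once the alert is displayed, so it does not show how a repeat would first qualify a patient. That is fair as to mechanism. It does not close the rule, which would accept any two values from one visit however they were recorded.

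**Acute-care values.** No passage says that emergency or inpatient readings enter the search. The network includes hospital-based practices, but the reference to "self-report at the time of hospital registration" concerns race and ethnicity and proves nothing about vital signs. This stands: the hospital-stay scenario is an assumption. No passage excludes it either.

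**Existing safeguards.** The Section III rule, the 90-day eGFR spacing, the 150-chart review and the intended alignment of the CKD rules with a national standard all reduce the problem. They do, but none states a setting or distinct-date condition for SBP.

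**The figures.** The reading counts and SDs are assumed, and both push the contrast the same way. Readings within a stay are correlated, so independence may overstate the chances. The results also apply only to patients who had a stay. All of this stands, and the figures show direction only.

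**Stronger readings that a reader might infer.** One is that a single acute illness can create CKD by eGFR; the 90-day separation rules this out for an illness shorter than that. Another is that one hospital stay qualifies a patient under every version of the SBP rule; Section III's enrollment-visit condition prevents it. A third is that the trial is biased between arms; the criteria are the same in both arms, so the gap alone does not show this.

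**Conclusion.** The point holds in limited form. The Aim 2a SBP rule, followed as written, can enroll a patient on readings from one occasion. Under Section III an acute-care value can only replace the single prior reading, leaving one raised reading at enrollment. For CKD, the open routes are two separate acute episodes by eGFR and an unspaced UACR pair.

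The consequence is some dilution of the SBP contrast and some mislabelling as uncontrolled hypertension or CKD. The size is unknown. It depends on which SBP rule is built, whether acute-care values are searched, and how many patients qualify only through them. None of this can be settled from the documents, and the sample-size multipliers above should not be cited as estimates. The change is worth making before launch because it is cheap then and hard to repair once patients are enrolled.

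**What to change.** 1. Reconcile the SBP rules in Section III and the Aim 2a procedures: one prior reading plus the enrollment visit, or any two readings; and two years before the enrollment visit, two years before the study period, or one year before the visit. Reconcile the two-year and five-year record windows as well.
2. In whichever rule is kept, count only SBP, eGFR and UACR values from outpatient encounters, excluding emergency, inpatient and procedural settings.
3. Require the qualifying SBP readings to fall on different calendar dates.
4. State whether the 90-day spacing applies to the UACR pair.
5. Build the conditions identically in the live and silent alerts, and add setting and date checks to the planned 150-chart review.
6. Re-run the EHR count of 2,350 under the final rule. The same query can report how many patients qualify only through acute-care or same-day values, which would supply the missing size.

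The cost is an encounter-type filter, a distinct-date condition and one repeat query. The downside is a somewhat smaller eligible pool.

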#### **Inclusion of Women and Minorities**

Women will be represented in this study, reflecting the patient population of the BWH primary care practices and the physician population of BWH; women comprise over 50% of patients in these practices. Minorities also are fully represented in this study in proportion to their presence in these primary care practices and in proportion to their presence in the BWH physician and specialist community. The practices serve an ethnically and socioeconomically diverse patient population. Approximately 16% percent of BWH patients are Latino and 29% are Black. About 1.5% of BWH patients are Asian. Definitions of patients' race and ethnicity will be based on self-report at the time of hospital registration. By promoting uniformly high standards of patient care, our interventions may lessen disparities in care.

### IV. SUBJECT ENROLLMENT

Randomization and Enrollment: This study will utilize a matched-pair cluster randomized design with the intervention on the cluster level, and the main outcome (6 month minus baseline change in SBP) measured at the patient level. We will have 174 clusters (made up of 185 clinicians) in the study. We will match pairs of clusters with similar number of patients and prior year mean blood pressure of patients in the cluster. One cluster in each pair will be randomized to the intervention and unit one to usual care. Patients will be electronically identified and included in the study over the course of 12 months. Patients seen by PCPs during the pilot study will be excluded. Retrospective data indicates that 70% of patients have a follow-up around 6 months. Outcomes assessment will occur at 180 days (+/- 60 days). After the 12-month enrollment period ends, data collection will continue for 6 months so that those enrolled toward the end of the enrollment period will have a full 6 months to complete any interventions ordered by the PCP. A small subset of PCPs will be enrolled in a pilot study for approximately one month, as described below in study procedures Aim 1b. Clinical outcomes will be recorded and reviewed every month over the course of the trial.

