Implementation of CDS in Epic: The next step is implementation in Epic as a BPA. Each of the rules will be added to the Epic database. The BPAs appear in an area of the screen that is visible when orders are being entered. Currently, there are several cancer screening BPAs and a seasonal influenza BPA. The CDS will be moved to the Production environment in “silent mode” before the scheduled start date of the trial, where it will record when it would fire, but it will not be displayed to the user. This step will allow us to validate that the rules are accurately identifying patients and producing the correct recommendations through a chart review. We will review 10 charts of patients with CKD and uncontrolled HTN per clinic for a total of 150 charts. The CDS will be activated in the Production environment on the start date of the clinical trial in Aim 2.

Validation of Hypertension-specific Process Measures: In preparation for the clinical trial in Aim 2, we will validate three process measures. Two of the measures will reflect treatment intensification by the PCP, 1) an increase in dosage or 2) addition of a new anti-hypertensive agent. The third measure will reflect medication adherence by the patient using data from a pharmacy benefits manager. We will perform a retrospective chart review of 150 charts to calculate the sensitivity and specificity of each rule.

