you do X?" and "What would you change about the content of the CDS?" The moderator and observer will manually record observations during the testing session. In addition to the comments and data recorded during the session, usability metrics will be coded after the session using Morae software. Usability metrics are measurements collected to determine to what extent usability goals have been met. The metrics will include task completion success rates, time-on-task, error rates, and assists by the moderator. We will be able to compare these measurements to those gathered from subsequent tests to determine whether iterative changes to the CDS have improved the usability of the CDS. Qualitative analysis: Qualitative methods will be employed to analyze the data. The research assistant will review the video recordings to identify usability issues based on observations of the participants during the task and the participants' think-aloud comments. Video recordings will be transcribed verbatim, and subject identifiers will be removed from the transcripts. The transcripts will be organized by task and participant and then quotes will be identified that illustrate a user expectation, frustration, or misinterpretation of content or functionality.

Pilot Study: Prior to the clinical trial, a pilot study will be conducted in live clinical settings. A subgroup of PCPs will be selected and the BPAs will be turned on for approximately one month. Interaction with the BPAs will be monitored. Each time a BPA fires the research team will contact the PCP by email to gather feedback through surveys and/or interviews. Iterative refinement of BPAs may be undertaken.

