## VI. BIOSTATISTICAL ANALYSIS

Data collected during the pilot study will not be included in the final analysis. Patients enrolled in the pilot study will not be enrolled in the final analysis. However, PCPs in the pilot study will be included in the intervention arm of the main clinical trial. A subgroup analysis will be performed on patients of these PCPs.

Table 1. Outcome Variables and Measures for Both Arms

Measurement Variable	Form of Variable	Analysis Metric	Time Point
Primary			
Mean SBP	Continuous	Change from baseline	6 months, 12 months, 18 months
Secondary			
Controlled SBP Rate	Dichotomous	Proportion of patients with controlled SBP rate	6 months, 12 months, 18 months
Urine Albumin to Creatinine Ratio	Continuous	Urine Albumin to Creatinine Ratio	6 months, 12 months, 18 months
Serum Creatinine > 2.0	Dichotomous	Proportion of patients with Creatinine > 2.0	Monthly
eGFR	Continuous	eGFR	6 months, 12 months, 18 months

Medication ordered	Dichotomous	Proportion of patients with recommended medication ordered	6 months
Basic metabolic panel ordered	Dichotomous	Proportion of patients with basic metabolic panel ordered	6 months
Referral to e-consults	Dichotomous	Proportion of patients with referral to e-consults	6 months
BPA acceptance	Dichotomous	Proportion of patients where BPA was accepted	6 months
Mean SBP of less than 110	Dichotomous	Proportion of patients with mean SBP of less than 110	Monthly
Newly documented allergy	Dichotomous	Proportion of patients with newly documented allergy due to adverse drug events	Monthly
K+ > 5.2	Dichotomous	Proportion of patients with K+ > 5.2	Monthly
K+ < 3.6	Dichotomous	Proportion of patients with K+ < 3.6	Monthly
Mean SBP intent-to-intervene analysis with imputation of missing 6-month BP measurement	Dichotomous	Proportion of patients with missing 6-month BP measurement	6 months
Controlled SBP Rate intent-to-intervene analysis with imputation of missing 6-month BP measurement	Dichotomous	Proportion of patients with missing 6-month BP measurement	6 months

Table 2. Outcome Variables and Measures for Intervention Arm Only

Measurement Variable	Form of Variable	Analysis Metric	Time Point
Acknowledgment reason entered	Dichotomous	Proportion of patients with acknowledgment reason entered	6 months
Feedback button clicked	Dichotomous	Proportion of patients with feedback button clicked	6 months

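### The pilot-month exclusion falls only on intervention clusters and modestly depletes frequent attenders on one side of the pairs that contain a pilot PCP

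*Combined protocol and SAP*

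**What the plan says.** The design is set out in Section IV (Subject Enrollment): "This study will utilize a matched-pair cluster randomized design with the intervention on the cluster level". Pairs are matched on number of patients and prior-year mean blood pressure, and one cluster of each pair is randomized to the intervention.

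On the pilot, Section IV says "A small subset of PCPs will be enrolled in a pilot study for approximately one month". The Aim 1b procedure in Section V adds that "A subgroup of PCPs will be selected and the BPAs will be turned on for approximately one month". The number of pilot PCPs is not given.

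The exclusion appears twice, in different terms. Section IV: "Patients seen by PCPs during the pilot study will be excluded". Section VI (Biostatistical Analysis): "Patients enrolled in the pilot study will not be enrolled in the final analysis". Section VI then says that "PCPs in the pilot study will be included in the intervention arm of the main clinical trial" and plans a subgroup analysis of those PCPs' patients.

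For controls, the Aim 1 and 1a procedures say that patients are identified by the same inclusion criteria through an alert running silently. The only exclusion named there is pregnancy. No section applies a pilot-month exclusion to control PCPs or to the matched partners of pilot PCPs.

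**The concern.** Keeping patients already exposed to the live alerts out of the main trial is sensible. The difficulty is that the rule acts in one arm. A patient of a pilot PCP who attends in the pilot month is lost to the trial. A patient of the matched control PCP who attends in the same month stays eligible.

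Attendance in a given month is more likely for people who attend often, so the patients left in pilot clusters are, on average, less frequent attenders than those in the partner cluster. Enrollment is triggered by a visit, and the 6-month blood pressure needs a further visit (Section IV expects about 70% to have one). A difference in visit frequency created before the intervention starts could therefore affect case mix and outcome availability in those pairs.

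**Working it through.** The plan gives no figure to reproduce here. The check has two parts: which arm the rule reaches, and how far it could shift visit frequency.

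**Reach.** Section IV excludes patients seen in the pilot. Section VI excludes patients enrolled in it and places its PCPs in the intervention arm. Nothing mirrors this for controls. The natural combined reading is exclusion from intervention clusters only.

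**Inputs from the documents.** 2,350 patients (Aim 2a); 174 clusters and 185 clinicians (Section IV); a pilot of about one month. Hence 2,350/185 = 12.7 patients per clinician, 2,350/174 = 13.5 per cluster, 2,350/2 = 1,175 per arm and 185/2 = 92.5 clinicians per arm.

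**Assumptions.** Visits are Poisson. Patients' yearly rates follow a gamma distribution with shape 2 and mean m = 3, 4 or 6. There are 5 to 20 pilot PCPs with average panels.

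**If any visit counts.** The share removed is 1 − (1 + m/24)^−2. The mean rate among those kept is m/(1 + m/24). The control partner keeps everyone, so its mean is m.

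| m | Removed | Kept, mean visits/year | Partner | Difference |
|---|---|---|---|---|
| 3 | 21.0% | 2.67 | 3.0 | 11% lower |
| 4 | 26.5% | 3.43 | 4.0 | 14% lower |
| 6 | 36.0% | 4.80 | 6.0 | 20% lower |

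A simpler model agrees in direction. Take a panel half at 2 and half at 6 visits per year, and count only those with a visit in the 12-month enrollment window. The frequent group falls from 54% to 45% in pilot clusters and stays at 54% in partners.

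**Share of the arm.** Pilot PCPs/92.5 × share removed:
- Low: 5/92.5 × 0.210 = 1.1%, or 5 × 12.7 × 0.210 ≈ 13 patients.
- High: 20/92.5 × 0.360 = 7.8%, or 20 × 12.7 × 0.360 ≈ 91 patients.

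An average pilot cluster falls from 13.5 to between 13.5 × 0.64 = 8.6 and 13.5 × 0.79 = 10.7 patients.

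**If only alert-triggering visits count.** Assume a fraction q of visits meets the alert criteria, and count patients with at least one such visit in the 12 months after the pilot. With rate λ, the share removed is 1 − E[exp(−qλ/12) − exp(−13qλ/12)] / E[1 − exp(−qλ)].
- q = 0.3, m = 3: about 9% removed; kept 3.72 against 3.84 visits per year, 3% lower.
- q = 0.5, m = 6: about 23% removed; kept 6.02 against 6.69, 10% lower.

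**Possible effect on SBP.** The shift in the arm mean is the share removed × the difference in SBP change between removed and kept patients. For an illustrative 5 mmHg difference, it runs from 5 × 0.011 = 0.06 to 5 × 0.078 = 0.39 mmHg. Section I cites an average decision-support effect of 1 mmHg in a non-CKD population. The documents support neither the 5 mmHg nor its direction.

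**The case against.** **The rule may be symmetric.** Section IV says PCPs, not pilot PCPs. Taken literally, it could cover every PCP's patients seen in that month. Section VI, which speaks of patients enrolled in the pilot, makes the pilot-only reading more natural but does not settle it. This objection stands as a reason to clarify the wording first. If symmetry was intended, the text still has to say so.

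**The narrower wording removes fewer patients.** This is correct, and the any-visit figures are therefore upper ones. The exclusion would still fall on one arm.

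**The planned subgroup analysis deals with it.** That analysis makes the pilot PCPs' patients visible but does not restore comparability in the primary contrast.

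**Stronger readings are tempting but not supported.** In the any-visit model the removed patients average 4.26 to 8.13 visits per year against 2.67 to 4.80 for those kept, and a reader might infer a large imbalance within pairs. That is the wrong contrast: the arms differ by kept patients against all patients in the partner cluster, which is 11 to 20%. A reader might also infer that the matching is undone. The documents do not say when matching is done or which patients it counts, nothing shows that prior-year mean blood pressure is disturbed, and unequal cluster size within a pair is not itself bias.

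**Conclusion.** The point holds in a limited form. On the natural reading, a visit-dependent exclusion applies to intervention clusters only and modestly depletes frequent attenders in pairs that contain a pilot PCP. The any-visit range of 11 to 20% fewer visits, and the upper range of 1 to 8% of the intervention arm, rest on assumed visit rates and an assumed 5 to 20 pilot PCPs. Under the narrower rule the visit difference is about 3 to 10%, assuming 30 to 50% of visits meet the alert criteria. The effect on the overall SBP contrast is probably small and cannot be determined from the documents. A material bias in the primary result is not shown.

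A reader might also infer that placing pilot PCPs in the intervention arm breaks the randomization. That follows only if they were chosen before allocation. They could have been drawn from clusters already allocated to intervention, and the documents do not say which.

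**What to change.** 1. Reconcile *seen* (Section IV) with *enrolled* (Section VI) into one exclusion rule, and state whose patients it covers.
2. Apply that identical rule, for the same calendar period, to the control clusters matched to pilot PCPs. If any visit excludes a patient, any visit must count in the partner cluster; if only alert-triggering visits do, only those count. A retrospective EHR query is the safe source. The Aim 1 and 1a procedures describe a silent-mode version "where it will record when it would fire, but it will not be displayed to the user", but do not say that it logged control PCPs during the pilot month. Use that log only if it covers the period.
3. Prespecify a sensitivity analysis that omits every pair containing a pilot PCP. This also addresses non-random placement of pilot PCPs if they were chosen before allocation.

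The cost is a short change to the eligibility text, one query, one added analysis and the loss of a similar small number of control patients (about 1 to 8% of that arm under the same assumptions). Applying the same rule on both sides removes the selection difference that this rule creates.

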## II. SPECIFIC AIMS

**Hypothesis:** The mean systolic blood pressure of the CKD population can be decreased by an intervention with three innovative features: 1) methods to synthesize EHR data in order to identify under-diagnosed chronic conditions, 2) iterative improvement in CDS content through human factors methods to maximize the “informativeness” of the CDS, and 3) the use of behavioral economic principles to create behavioral “nudges” internal and external to the CDS.

**Specific Aim 1:** To develop and validate the intervention.

**Specific Aim 1a:** To develop and validate the CDS that will: 1) synthesize existing laboratory tests, medication orders, and vital sign data; 2) increase recognition of CKD, 3) increase recognition of uncontrolled HTN in CKD patients; and 4) deliver evidence-based CKD and HTN management recommendations.

**Specific Aim 1b:** To improve the design and content of the CDS using human factors methods, specifically usability testing.

**Specific Aim 1c:** To develop a “wrap-around” intervention including two behavioral “nudges”: 1) pre-checked default orders, and 2) an email to obtain commitment from PCPs to obtain their commitment to follow the CDS recommendations.

**Specific Aim 2:** To test the effectiveness of the intervention.

**Specific Aim 2a:** To evaluate whether the intervention developed in Aim 1 significantly decreases mean systolic blood pressure in a population of CKD patients with blood pressure  $> 140/90$ ,  $N=2,350$  ( $N$  derived from EHR data about primary care patients at 15 clinics). We will evaluate the effectiveness of the intervention in a pragmatic, cluster-randomized controlled trial, randomized at the level of the physician (185 PCPs). Secondary outcomes will include hypertension-specific process measures, such as treatment intensification.

**Specific Aim 2b:** To evaluate whether the intervention improves process measures for quality of CKD care including: documented CKD diagnosis, annual serum creatinine test, and annual urine albumin test. We will also examine process measures related to CKD care. We will use multivariable logistic regression to account for clustering by PCP using a multilevel statistical regression model, as implemented in the SAS package through the GLIMMIX procedure.

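### Data collection ends about two months before the 6-month SBP window closes for the last patients enrolled, so some valid late readings will not be captured

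*Combined protocol and SAP*

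**What the plan says.** All the timing rules stand together in Section IV (Subject Enrollment) of the combined protocol and SAP.

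- Primary outcome: "the main outcome (6 month minus baseline change in SBP) measured at the patient level".
- Window: "Outcomes assessment will occur at 180 days (+/- 60 days"), which is day 120 to day 240, a width of 120 days.
- Enrolment: "Patients will be electronically identified and included in the study over the course of 12 months".
- End of collection, once enrolment has closed: "data collection will continue for 6 months so that those enrolled toward the end of the enrollment period will have a full 6 months". The reason given is that late enrollees "will have a full 6 months to complete any interventions ordered by the PCP". The upper limit of the outcome window is not mentioned.
- Expected follow-up: "Retrospective data indicates that 70% of patients have a follow-up around 6 months".

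Table 1 in Section VI lists mean SBP, as change from baseline, at 6, 12 and 18 months. It does not say whether these count from each patient's enrolment or from the start of the trial. It lists an analysis that imputes a missing 6-month blood pressure, but only among the secondary outcomes. No section gives a later extraction date or a rule for patients enrolled near the end.

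**The concern.** The collection period after enrolment was sized to the nominal 6 months, while the outcome definition accepts readings up to 60 days beyond that. The two rules cannot both be met for patients enrolled near the end.

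This matters because the trial is pragmatic and describes no scheduled study visit for blood pressure. A patient has a primary outcome only if he or she returns within the window. A shorter window therefore means more patients without an outcome, and those who are measured are measured earlier on average. The plan already expects about 30% to lack a reading around 6 months, so this adds avoidable missing data on the primary endpoint.

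**Working it through.** **Inputs.** From Section IV: enrolment period E = 12 months (360 to 365 days); further collection P = 6 months (180 to 184 days); window day 120 to day 240; follow-up 70%. From Section II, Aim 2a: N = 2,350. The documents give no enrolment curve or visit rate, so those below are assumptions. I also assume that the 70% refers to the full 120-day window; Section IV says only that it is around 6 months.

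**1. Reproduce the plan's figure.** A patient enrolled on day e has E + P − e days of follow-up. For the last patient e = E, which leaves P = 180 to 184 days. The stated full 6 months is reproduced.

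**2. Window lost.** Days lost = max(0, 240 − (E + P − e)). This is above zero for patients enrolled in the last 240 − P = 56 to 60 days.

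- Largest loss (last patient): 56/120 = 47% to 60/120 = 50%.
- Average among those affected, since the loss rises linearly from zero: 23% to 25%.

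**3. Share affected if enrolment is even (assumption).** 56/365 = 15.3% to 60/360 = 16.7%, or about 360 to 392 of 2,350. Over the whole trial, 15.3% × 23.3% = 3.6% to 16.7% × 25% = 4.2% of window days are lost.

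**4. Effect on follow-up if enrolment is even.** Two simple visit models, both set to give 70% in a full window:

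- *Constant visit rate* (365-day enrolment, 57 to 60 affected days). Rate = −ln(0.3)/120 per day = 3.66 per year. Follow-up in a window of w days = 1 − 0.3^(w/120). For the last patient this is 1 − 0.3^(60/120) = 45% to 1 − 0.3^(63/120) = 47%. Averaged over affected patients it is 59% to 60%. Overall, with 60 days lost: 70% − 16.4% × (70% − 58.8%) = 68.2%. This is about 38 to 43 fewer measured patients.
- *The 70% spread evenly over day 120 to 240.* Last patient: 70% × (1 − 0.50) = 35%, up to 37%. Affected patients: 52% to 54%. Overall: about 67%, or 59 to 69 fewer measured patients.

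**5. Effect if enrolment is front-loaded.** Section III enrols a patient at a visit with SBP above 140 mmHg. With visits at 3.66 per year, many eligible patients would be caught early in the 12 months. Let r = 3.66/365 per day, let a fraction q of visits qualify (assumption), and let D be the number of affected days (57 to 60). Then

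share enrolled in the last D days = [exp(−q·r·(365 − D)) − exp(−q·r·365)] / [1 − exp(−q·r·365)].

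For q = 1 and D = 60: (0.0469 − 0.0257)/(1 − 0.0257) = 2.2%. Weighting the constant-rate follow-up of step 4 by this enrolment curve gives:

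| Visits that qualify (q) | Patients affected | Fall in overall follow-up |
|---|---|---|
| all | 2.0% to 2.2% | about 0.2 points |
| half | 6.3% to 6.7% | 0.6 to 0.7 points |
| a quarter | 10% to 11% | 1.0 to 1.2 points |

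**6. After the change.** With P = 240 the days lost are max(0, e − E) = 0 for every patient.

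**The case against.** The strongest reply is that the effect is small. Day 180 is within reach of every patient, and only the late tolerance is trimmed. The 50% figure belongs to the last patient alone, and even under even enrolment the trial loses about 4% of window days. This stands, and it limits the weight of the point. It does not remove the mismatch: the protocol chose to accept readings to day 240 and then does not collect some of them.

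A second reply is Table 1. If its 12 and 18 months count from each patient's enrolment, collection must run well past day 240 and the truncation disappears. But that reading contradicts Section IV, because late enrollees could not reach month 12 or 18. Counted from trial start, 18 months equals 12 + 6 and confirms the cut-off. The documents do not settle it, so the two places need reconciling either way.

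A third reply is that missing readings are to be imputed. That is planned only as a secondary analysis, and imputing a reading that a later extraction would supply is the weaker course.

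A reader might infer two stronger points that the documents do not support.

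- *Bias between arms.* The alert is displayed only in the intervention arm, so one might suppose that it changes when patients return. Section V describes recommendations on medication, adherence, laboratory tests and handouts, and a pledge email, but no recall or early-return prompt. Both arms share one calendar, and controls are identified in real time by the same criteria.
- *Every return visit from day 184 to day 240 counted as missing.* This is true only of the last enrollees, and only if they have no other reading from day 120 to the cut. For the other affected patients the cut falls later in that interval.

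**Conclusion.** The point holds as a modest, avoidable loss of primary-outcome data. As Section IV is written, patients enrolled in about the last 56 to 60 days cannot be observed to the end of the stated window. They lose between 0 and about 50% of it.

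The calendar arithmetic needs no assumption beyond the length of a month. The size in patients does. Under even enrolment about 16% are affected and follow-up falls from 70% to about 68% (67% if visits are spread evenly over the window). The front-loaded cases, which fit enrolment at a qualifying visit, give about 2% to 11% affected and 0.2 to 1.2 points. The true figure depends on the enrolment curve, which the documents do not give. The conclusion also assumes that Table 1 does not imply longer collection per patient. The effects supported are more missing outcomes and earlier measurement in late enrollees; a difference between arms is not shown.

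**What to change.** Change Section IV so that EHR data collection for the 6-month SBP continues until 240 days after the last enrolment, about 8 months after enrolment closes. State the time origin of the 6-, 12- and 18-month points in Table 1 and make it agree with that collection period.

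The cost is one amended sentence, a clarification to Table 1, and an extraction and data lock about two months later. No extra visits or patients are needed.

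Closing enrolment for the primary analysis 240 days before the present data cut is not a good substitute. Under even enrolment it would drop 2,350 × 57/365 = 367 to 2,350 × 60/365 = 386 patients. At the 59% to 60% follow-up of the constant-rate model, about 218 to 227 of them would have a measured outcome. That is a poor exchange for avoiding about 38 to 43 missing ones.
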